It is estimated to take up to 1 year to recruit participants for this study. It will take approximately 3 years to complete the study and all data analyses. Participation in this study will take approximately 3-4 weeks. The length of participation is virtually identical for participants who complete Phase I and II vs. Phase II only. This is due to Phase I including about one to two hours of laboratory-based procedures prior to participants being trained and asked to use the FoodImage app to track food waste for 4 to 7 days over the subsequent week. Participants who only complete Phase II will not conduct the laboratory-based procedures but all other procedures will be identical.

Study Endpoints

The primary endpoint of this study is food waste and food waste behavior. We will explore these endpoints via the following aims and objectives:

- Development of FoodImage, a smartphone app that measures household food waste and food-waste-related behaviors; and assess differences in the accuracy, time burden of, and perceived convenience of measurements taken with the FoodImage app versus the current state-of-the-art household food waste measurement approach (a pen-and-paper diary) with and without a food scale
- Use the FoodImage app in a pilot randomized controlled trial designed to evaluate the effectiveness of reducing household food waste through behavioral nudges in the form of personalized feedback about food waste levels and household-specific reduction goals.

All data from the FoodImage app (including home address and GPS coordinates from food images) will be used as a study endpoint.

Procedures and Visit Description

The study will accomplish three activities:

- 1) Development of the FoodImage Smartphone app
- 2) Testing the FoodImage app with consumers in a lab setting (Phase I)
- 3) Randomized Controlled Trial of behavioral nudges to reduce household food waste (Phase II)

FoodImage App Development

The programming and development team that created a previous app called SmartIntake® agreed to build the FoodImage app. Originally, we expected the FoodImage app to rely on some features of the SmartIntake app, though FoodImage was ultimately built from scratch. The FoodImage app sends participants' images and accompanying data (e.g., receipts, food descriptions, Participant ID number, and timestamp) to a secure PBRC server where a team will analyze the images to estimate food waste.

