The coverage and capabilities that will distinguish the FoodImage app from the SmartIntake® app will include:

- A. **Comprehensive measurement of food waste.** The FoodImage app will quantify food waste at all stages where food waste occurs at the consumer level (e.g., left-overs after a meal, cabinet or refrigerator/freezer purges, food preparation, etc.). The existing SmartIntake® app quantifies *plate* waste that is present at the end of meals and this is used to calculate food intake (food intake = food selection minus plate waste). SmartIntake® does not, however, determine if the plate waste was discarded, saved to eat later, etc., thus, it cannot determine if *plate* waste is *food* waste.
- B. **Receipt scanning capability.** An exploratory module will be developed in which receipts from food purchases are scanned. This will provide the potential to calculate the dollar value loss of waste using prices actually paid by the participant. While this module is exploratory and not primary, it holds promise for assessing the exact purchase value of food waste and for exploring hypotheses that link food acquisition price to eventual food consumption and food waste.

Phase I (Overview)

Phase I of this study will consist of testing the FoodImage App with participants in a lab setting. The primary purpose of Phase I will be to test the measurement features of the FoodImage app under controlled conditions and to obtain user satisfaction data about the app. Participants will use three methods in the lab setting:

- 1) the FoodImage app,
- 2) a pen-and-paper record, where the participant will visually estimate portion sizes, and
- 3) a pen-and-paper record, where the participant will use a kitchen scale to weigh the foods.

Participants will be randomly assigned to the order in which these methods will be used, as described below. It is noted that, by necessity, the last method that will be used is a pen-and-paper record with a kitchen scale since this procedure will cue participants to the actual weight of the foods and corrupt their visual estimates, should the visual estimation procedure occur after the method that relies on a kitchen scale. Thus, the order in which participants first use FoodImage vs. a pen-and-paper record with visual estimates of portion size will be counterbalanced. The two orders that will be balanced among participants are:

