- *User Satisfaction Survey*- This survey asks questions to help staff understand participants' satisfaction with using an iPhone app (FoodImage) to take and send photos of food waste (Appendix B.2.c).

- *Food Environment Questionnaire*- This questionnaire asks questions about purchasing food for the household (Appendix B.2.d).
- *Waste Toss Methods Questionnaire*- This questionnaire asks questions about how participants typically dispose of food in their household (Appendix B.2.e).
- *Food Waste Tip Questionnaire* – This questionnaire asks questions to help staff understand participants' satisfaction with receiving training tips to help reduce food waste (Appendix B.3.a).

Data Analysis and Specimen Management

Phase I analysis objectives include:

- 1) Determining if food waste measured with the FoodImage app is equivalent to the criterion value (directly weighed food waste) for each source (plate waste, food purges, etc.). Error (the difference between food waste measured with the FoodImage app and the criterion value) will also be quantified for each source.
- 2) Determining if food waste measured with each of the pen-and-paper diary methods (with and without a kitchen scale) is equivalent to the criterion value for each source. Error will also be quantified for each source.
- 3) Determining if the error from the FoodImage app is smaller than error from the pen-and-paper records.
- 4) Determining if satisfaction ratings differ significantly between the app and the pen-and-paper record approaches.
- 5) Determining if the amount of time respondents took to complete measurements differed between the app and diary approaches.
- 6) Qualitative assessments by respondents of the desirable and undesirable features of the app and pen-and-paper records.
- 7) Determining if the variance of waste measures differed between the app and pen-and-paper record approaches.
- 8) Assessing the accuracy of receipt data as captured by participants using the app.

Power Analysis. We base our power analysis on plate waste data gathered from previous research conducted at PBRC [20]. With an N of 24, we are powered to detect equivalence within 20 grams with power of 0.80 and alpha of 0.05. Also, *t*-tests to determine if the error from the app (weighed food waste minus estimated waste) differs significantly from the error from the diary method is powered to detect differences as small as 12.8 grams.

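### Phase I randomises the order of app and visual diary, but the stated comparison has no order or period term; a sizeable shift between first and second use would cost power, and adjusting for it is nearly free

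*Combined protocol and SAP*

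**What the plan says.** Phase I (Overview) has every participant use the app, a visually estimated paper record and a paper record with a kitchen scale. Two orders are listed and assigned at random. They differ only in whether the app or the visual record comes first: "Thus, the order in which participants first use FoodImage vs. a pen-and-paper record with visual estimates of portion size will be counterbalanced". The third position is fixed: "the last method that will be used is a pen-and-paper record with a kitchen scale". The reason given is that weighing would reveal true weights and spoil later visual estimates.

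Under Data Analysis and Specimen Management, Phase I objective 3 asks whether app error is smaller than pen-and-paper error, and objective 5 asks whether completion time differs. Neither objective names a model. The only named test of the error difference is in the Power Analysis paragraph, which says that a t-test of whether app error (weighed minus estimated waste) "differs significantly from the error from the diary method is powered to detect differences as small as 12.8 grams". The sentence before it reads "With an N of 24, we are powered to detect equivalence within 20 grams with power of 0.80 and alpha of 0.05". No SD is given, only a citation to earlier plate-waste data. The text does not say whether the t-test is paired or one- or two-sided, or whether the diary meant is the visual one, the scale one or both. Order, period and sequence are not mentioned in the analysis text.

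**The concern.** For app versus visual diary, the design is a two-period, two-sequence crossover. Counterbalancing protects the mean difference, but it does not take order variation out of the error term. If participants do better or worse the second time they record the same foods, the paired difference moves up in one order and down by the same amount in the other. A t-test without an order term treats that systematic spread as noise.

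What is at stake is power for a stated Phase I hypothesis, with 24 people and no allowance above 0.80. If unusable records left the two orders unequal, part of the shift would also enter the estimate. The design already pays for the information needed to prevent both, because order is randomised and known for every participant.

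**Working it through.** **Inputs from the documents.** N = 24; detectable difference 12.8 g; power 0.80 and alpha 0.05 (stated for the equivalence test and assumed to carry over to the t-test); two balanced orders, taken as 12 and 12.

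**Inputs assumed.** Paired, two-sided test; no order variation in the planning SD; a shift π (g) in error from first to second use, common to both methods. The documents give no value for π, so a range is shown.

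**Step 1: the plan's figure.** Without an SD, 12.8 g cannot be reproduced, only solved backwards. Setting noncentral-t power to 0.80 with 23 df and noncentrality 12.8·√24/SD gives SD = 21.4 g. Other readings:

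- paired, two-sided, normal approximation: 22.4 g
- paired, one-sided: 24.5 g (t) or 25.2 g (normal)
- two-sample, normal approximation: 15.8 g (24 per group) or 11.2 g (12 per group)

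**Step 2: effect of leaving order out.** With method difference τ, the paired difference has mean τ + π in one order and τ − π in the other. With 12 per order the overall mean is still τ. The expected sample variance becomes SD² + π²·24/23. For π = 10 this is 459.4 + 104.3 = 563.7, an SD of 23.7 g instead of 21.4 g.

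**Step 3: power.** The power of the unadjusted test was found by integrating over the noncentral chi-square distribution of the sample variance.

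| Shift π (g) | Power at 12.8 g, no order term | Difference detectable with power 0.80 (g) | Type I error |
|---|---|---|---|
| 0 | 0.800 | 12.80 | 0.050 |
| 2.5 | 0.796 | 12.87 | 0.049 |
| 5 | 0.784 | 13.06 | 0.044 |
| 10 | 0.734 | 13.80 | 0.031 |
| 15 | 0.650 | 14.92 | 0.017 |
| 20 | 0.534 | 16.32 | 0.008 |

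Simulation with 100,000 runs per case agrees: 0.784, 0.736 and 0.534 at 5, 10 and 20 g.

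**Step 4: with the term.** Using the pooled within-order variance (22 df), power at 12.8 g is 0.798 and the detectable difference is 12.83 g, whatever the size of a common shift. The break-even point is π of about 1.6 g. Below it the unadjusted test is ahead by at most 0.002 in power.

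**Step 5: shift in one method only.** If only the diary shifts, by s, the paired difference moves by s in one order and 0 in the other. That is ± s/2 about its mean, so π = s/2. The 10 g row then needs a diary shift of 20 g, and the 20 g row one of 40 g. The contrast is averaged over first and second use.

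**Step 6: unequal orders.** Bias in the unadjusted mean is π·(n1 − n2)/(n1 + n2). At π = 10 g this is 10·1/23 = 0.43 g for 12/11, 10·3/21 = 1.4 g for 12/9 and 10·4/24 = 1.7 g for 14/10.

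**The case against.** Much of the case on the other side stands.

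- **The shift is hypothetical and may be small.** The documents never mention a practice effect or give its size. App images go "to a secure PBRC server where a team will analyze the images to estimate food waste", so participants' practice has little direct route to the app's gram values, and a shift confined to the diary acts at half size. No feedback on true weight is described between the app and the visual diary.
- **The SD is back-solved.** If the source SD already contained order variation, the unadjusted test keeps its 12.8 g. Adjustment would then be a gain: power 0.82 if π = 5 g and 0.89 if π = 10 g.
- **The plan is silent on order.** The t-test appears in a power paragraph. A reader might infer that the plan has decided to ignore order, but the text supports only that adjustment is not specified.
- **There is no inflation of false positives.** With balanced orders the estimate is unbiased and the test is conservative. A reader might infer a biased app-versus-visual-diary result. That would need unequal orders, which the protocol does not plan, and the bias would be small (step 6).

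These points limit the size of the problem. They do not give a reason to leave out the factor that was randomised. The half-size argument is also weaker for completion time, which participants generate with both methods and for which no test is named.

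**Conclusion.** The point holds as a gap in specification with a cheap remedy. No order or period term is named for a comparison whose order is randomised, and a sizeable shift between first and second use would take power at 12.8 g below 0.80.

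A reader might go further and conclude that any practice effect destroys the stated 12.8 g sensitivity. The documents do not support that. At 5 g the loss is 1.6 percentage points and the detectable difference is 13.06 g. Power stays within two points of 0.80 until the shift is about 5.5 g, and the loss becomes material at about 10 g, roughly half the back-solved SD. These figures rest on a paired two-sided test, an SD of 21.4 g free of order variation, a 12/12 split and a shift common to both methods.

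The comparison of the app with the scale diary is a separate matter. The scale diary is always last, so that contrast is confounded with position, and a period term for the first two methods does not remove this.

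**What to change.** Add to the Phase I analysis text:

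- Compare app and visual-diary error within participant, with method and period as fixed effects and participant as a random effect (or the equivalent order-adjusted paired test). Do the same for completion time. Report the estimated period effect.
- State the SD of the paired difference behind 12.8 g, whether the test is one- or two-sided, and which diary it refers to.
- Report the app-versus-scale-diary comparison with the limit that method and position cannot be separated.

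The cost is a few sentences and one degree of freedom (power 0.798 instead of 0.800 if there is no order effect). No participants, visits or data are added. Setting the model in advance also prevents a later choice between adjusted and unadjusted results.

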Phase II of this study is a randomized controlled trial of behavioral nudges via the FoodImage app to reduce household food waste. Phase II will occur in participants' natural environment (free-living conditions) and will include the 24 participants enrolled in Phase I and an additional 20 participants. Phase II, participants will be trained to use the FoodImage app to capture data on food purchases, food waste that occurs during food preparation, food waste that is present after eating, and food waste from food purges in free-living conditions. During data collection, subjects will record the source, reason, and destination of all food waste in the app.

Participants will use the app to collect food waste data for approximately 4 to 7 days over the first week of Phase II and these data serve as baseline data. Participants will then be provided with approximately a one-week break where they will not use the app to track food waste (or do any other study procedures). After the one-week break, participants will return to the center and will be randomly assigned (1:1 ratio) to one of the following groups:

1. Stress Management (Control Group). These participants will use the app to record food waste for approximately 4 to 7 days over the subsequent week. They will also receive information on stress management (Appendix C.1).
2. Food Saver (Intervention Group). These participants also will use the app to record food waste for approximately 4 to 7 days over the subsequent week. They will also be provided with the following:
 - a. Feedback on the amount of food waste their household created during the first week,
 - b. A goal to reduce the next week's food waste by 20% or more, and
 - c. Tips on how to reduce household food waste adapted from current consumer campaigns (e.g., Food: Too Good to Waste Implementation Guide and Toolkit, EPA 2016). This includes advice to limit purchases of unnecessary foods, donate or freeze unwanted and unspoiled foods, prioritize keeping and then eating left-overs, minimize waste during food preparation by preparing and serving smaller portions, purchase only needed foods, and purchase foods that are not near the expiration date (see Appendix C.2). A PBRC staff member will deliver tips to each respondent in this group via in-person and remote sessions (call, text, email, videoconference etc.).

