It is hypothesized that food waste will be equivalent (within 20 grams) when measured with the app vs. direct weights of food waste, while food waste measured with the diary method will not be equivalent to directly weighed food waste. It is also hypothesized that the error from the app will be significantly smaller than error from the diary method.

Phase II analysis objectives include:

- 1) Quantifying baseline distributions for total weight of household food waste

- 2) Determining the effectiveness of the behavioral nudge in altering
 - a) Total daily weight of household food waste,
 - b) Total daily weight of each source of household food waste by occasion, including
 - i) plate waste,
 - ii) food prep waste,
 - iii) purge waste,
 - c) Total daily weight of each source of food waste by food type (e.g., dairy, meat, fruits, etc.) and by macronutrient,
 - d) Daily percent of served food that is wasted, and
 - e) Total amount of food purchased by weight and value.
- 3) Quantifying satisfaction levels with the FoodImage app as measured in Appendix B.1.a. (User Preference Survey) and Appendix B.2.c (User Satisfaction Survey),
- 4) The demographic, household and attitudinal factors measured in Appendix B.2.d (Food Environment Questionnaire) related to
 - a) Effectiveness of the behavioral nudge intervention in reducing food waste generated and all subcomponents listed above, and
 - b) Satisfaction levels with the app as measured in Appendix B.2.c (User Satisfaction Survey).

Withdrawal of Subjects

Subjects may be withdrawn from the study if they are non-compliant with study procedures and they will be notified of their withdrawal via telephone or mail. Subjects may voluntarily withdraw from the study at any time. No additional data will be collected and they will be considered drop outs in the study.

Risks to Subjects

This study involves no greater than minimal risk. The main risk is breach of confidentiality, and the PBRC team will work to minimize this during data collection, handling, and analysis.

Potential Benefits to Subjects

Participants may benefit by increased awareness of their food waste behaviors.

Setting

All research procedures will be conducted at PBRC and in participants' natural environment.

Resources Available

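### Phase II recording days are neither fixed nor matched across weeks, and only Food Saver has a goal worded on the week's amount, so day choice could pass for waste reduction

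*Combined protocol and SAP*

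**What the plan says.** Under Phase II (Overview) in the combined protocol and SAP, the baseline instruction is: "Participants will use the app to collect food waste data for approximately 4 to 7 days over the first week of Phase II". After randomisation, control and Food Saver participants alike are to "use the app to record food waste for approximately 4 to 7 days over the subsequent week". The visit descriptions and Table 1 repeat the range. None of these places says who picks the days, links the follow-up days to the baseline days, sets a minimum number of valid days, or says how a day without entries is treated.

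Two elements are given to Food Saver alone. One is "Feedback on the amount of food waste their household created during the first week". The other is "A goal to reduce the next week's food waste by 20% or more". Neither is stated per recorded day.

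The first outcome in the Phase II analysis objectives is "Total daily weight of household food waste". The waste outcomes by source and food type are also daily weights, and another is a daily percentage. The denominator of a daily weight (recorded days or calendar days) is not defined. The amount of food purchased, by weight and value, is listed as a total and not as a daily figure.

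On completeness, the overview says: "During data collection, subjects will record the source, reason, and destination of all food waste in the app". The duty is tied to data collection, so a day inside the week on which the household does not record appears to comply.

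**The concern.** Follow-up recording days are settled after allocation, by participants who know their arm, and one arm has been given a figure to beat. Randomisation does not protect against a difference in recording that arises after it. No intent to mislead is needed: leaving the app aside on the day of a refrigerator clean-out would be enough.

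Two mechanisms need to be kept apart. Recording fewer days lowers weekly totals, and any daily figure divided by a fixed 7. Leaving out heavy days lowers even a mean taken over recorded days. If either happens more in Food Saver than in control, the artefact favours the hypothesis and cannot be separated from the intervention effect. No objective check on waste, such as weighed bins, is described for Phase II. Even without any difference between arms, comparing unlike sets of weekdays adds noise to the baseline-to-follow-up change in a trial of 44 people.

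**Working it through.** The plan states no Phase II effect size, SD or power, so there is no figure of its own to reproduce.

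**Inputs from the document.** 4 to 7 recording days in each period; a 20% goal in Food Saver; 44 participants at 1:1, so 22 per arm.

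**Assumed, because the document does not give them.** Day-to-day waste within a household is gamma distributed and independent, with a CV of 0.5 to 1.0; the baseline week is complete; true waste is unchanged.

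**Step 1: day count and the weekly total.** With *b* baseline days, *f* follow-up days and constant daily waste, the fall is 1 − f/b.

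| Baseline to follow-up days | Fall in recorded total | Meets 20% goal |
|---|---|---|
| 7 to 6 | 1 − 6/7 = 14.3% | no |
| 7 to 5 | 1 − 5/7 = 28.6% | yes |
| 7 to 4 | 1 − 4/7 = 42.9% | yes |
| 6 to 5 | 1 − 5/6 = 16.7% | no |
| 6 to 4 | 1 − 4/6 = 33.3% | yes |
| 5 to 4 | 1 − 4/5 = 20.0% | yes |

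All six pairs lie within the permitted range. If the unrecorded days are a random subset, the expected change in the mean over recorded days is 0%.

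**Step 2: selective omission and the mean over recorded days.** Simulated 7-day weeks (200,000 per CV), with the heaviest days removed:

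| Assumed daily CV | Heaviest day omitted | Lowest 4 of 7 kept |
|---|---|---|
| 0.5 | 12.6% | 30.6% |
| 0.8 | 21.0% | 47.2% |
| 1.0 | 26.5% | 57.0% |

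The last row can be checked by hand. At CV 1 the gamma is exponential, and with mean 1 the expected largest of 7 days is 1 + 1/2 + … + 1/7 = 2.593. The other six average (7 − 2.593)/6 = 0.735, a fall of 26.5%.

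**Step 3: from household to arm.** These falls apply to a household that selects in this way. If a share *p* of Food Saver does so, the arm's mean falls by about *p* times the figure. For one omitted day at CV 0.8, 0.25 × 21.0% = 5.3% and 0.50 × 21.0% = 10.5%.

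**Step 4: effect on a test.** A t-test on the log change in mean daily waste was simulated with 22 per arm, no true effect, within-household daily CV 0.75, between-household CV 0.6, two-sided 5% and 4,000 repeats. A significant false reduction appeared in 2.4% of trials with no selection, 13.7% if half of Food Saver omitted the heaviest day, and 42.2% if all did. The test is illustrative, since the plan names no analysis model.

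**The case against.** The strongest reply is that the waste outcomes are daily measures, so the 29% fall in a weekly total does not carry over to them, and meeting the goal on paper is not a trial outcome. That stands for a mean over recorded days. It does not cover a denominator of calendar days, which the text leaves open, or the total amount of food purchased. For those, the between-arm comparison is biased if the change in recorded days differs by arm.

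The plan also has safeguards. Staff keep in contact with participants to protect data quality and compliance (stated for the period after Visit 1). Both arms have refresher training at Visit 2, further contact until Visit 3 and a review of their data at Visit 3. Non-compliant participants may be withdrawn, and payment is for completing the phase and not for reaching the goal. These soften the risk, but none is a rule about days. The training and intervention appendices are not in the supplied text and might contain day instructions or per-day scaling. If so, the rule belongs in the protocol body too. A flexible window is also a defensible way to limit burden in a free-living pilot.

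Three stronger readings are tempting and should be resisted. A reader might infer that Food Saver households will select their days; the recording instructions are identical in both arms, and differential selection is possible but not shown. A reader might take the 13% to 27% as the expected bias; it is the ceiling for one omitted day and needs every Food Saver household to behave that way. A reader might compare it with a 20% target effect; the 20% is a goal handed to participants, and the plan states no Phase II effect size.

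**Conclusion.** The concern holds as a bias route that the plan permits, not as a bias shown to occur. The day-count arithmetic is certain: several permitted changes in recording days meet the goal, as worded on the week's amount, with no change in behaviour. Whether households would see it that way depends on how the feedback is presented, which the protocol does not say.

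For a mean over recorded days, bias requires heavy days to be left out more often in Food Saver, and its size is unknown. It rests on an assumed daily CV, assumed independent gamma days, a complete baseline week, the number of days omitted and the share of households doing it. Plausible partial selection (a quarter to a half of the arm, one day, CV 0.8) gives about 5% to 10%. The remedy is cheap and also removes weekday noise, so it is worth making.

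**What to change.** - Within the existing 4-to-7-day range, have staff assign each household's recording days at Visit 1 and repeat the same number and weekdays after Visit 2, in both arms. The visits are about 14 days apart, so the weekdays line up.
- Have participants confirm zero-waste days in the app. Treat an assigned day with neither an entry nor a confirmation as missing, not as zero; scoring it zero would deepen the bias.
- Define the daily outcome per recorded day, and express the feedback and the existing goal in the same unit. Scale the food-purchase total likewise or report it alongside the days recorded.
- Report the number of recorded days and the weekday mix by arm and period. Where days still differ, analyse at day level with a weekday/weekend term.

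The cost is scheduling text, a confirmation step in the app and a change of units in the feedback, with slightly less flexibility for participants. The number of recording days need not rise. The change does not prevent under-logging within an assigned day, or moving a clean-out to an unassigned one; both should be stated as limitations.
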